8.4.4 End of Study

Postvaccination Safety Follow-up Telephone Call (Day 90+7 and 180+7 after Last Vaccination)

Serious Adverse Event and AESI information will be collected for a total of 180 days (180+7 days) after administration of the last dose of study vaccine.

9 ADVERSE EVENTS

9.1 DEFINITIONS

9.1.1 Adverse Event

As per the ICH guideline (*Guidance for Industry, Clinical Safety Data Management: Definitions and Standards for Expedited Reporting – ICH-E2A*), an AE is any untoward medical occurrence in a patient or clinical investigation subject administered a pharmaceutical product and which does not necessarily have a causal relationship with this treatment. An AE can, therefore, be any unfavorable and unintended sign (including an abnormal, clinically significant laboratory finding), symptom, or disease temporally associated with the use of a medicinal (investigational) product, whether or not considered related to the medicinal (investigational) product.

The period of observation for all adverse events extends from the time the parent or legally appropriate representative gives informed consent until 28 days after the last vaccination (Exit Visit). The period of observation for serious adverse events and adverse events of special interest extends from the time the parent or legally appropriate representative gives informed consent until the end of study (180 days after the last vaccination) – see [Section 9.4](#) (Observation Period for Adverse Events) for further details.

Adverse events may include:

- Exacerbation (ie, an increase in the frequency or severity) of a preexisting condition. Illness present before study entry should be recorded in the medical history section of the eCRF and only be reported as an AE if there is an increase in the frequency or severity of the condition during the study.
- A clinical event occurring after consent but before the investigational product administration.
- Intercurrent illnesses with an onset after administration of the investigational product.

Adverse events do not include:

- Events identified at screening that meet exclusion criteria
- Medical or surgical procedures (the condition that leads to the procedure is the AE)
- Situations where an untoward medical occurrence has not taken place. For example:
 - Planned hospitalizations due to pre-existing conditions, which have not worsened.
 - Hospitalizations that occur for procedures not due to an AE (eg, cosmetic surgery).
 - Hospitalizations for a diagnostic procedure where the hospital stay is less than 24 hours in duration or for normal management procedures (eg, chemotherapy).
- Overdose of Investigational Product or any concomitant therapy that does not result in any adverse signs or symptoms.

9.1.1.1 Solicited AEs

Solicited AEs are those events specifically sought for and recorded by the parent(s)/guardian(s) in the 7-Day Diary, entered on the day of vaccination and the subsequent 6 days.

Solicited Local Reactions (Vaccination Site)

Solicited local reactions are defined and graded as follows:

Table 9.1.1.1-1 Solicited Local Reactions

Reaction	Intensity Grading			
	None (0)	Mild (Grade 1)	Moderate (Grade 2)	Severe (Grade 3)
Pain at the vaccination site	None	For subjects less than 36 months of age at the time of the first dose of study vaccine:		
		Minor reaction on touch	Cried/protected on touch	Cried when limb was moved/spontaneously painful
		For subjects 36 months of age and older at the time of the first dose of study vaccine:		
		Does not interfere with daily activities	Interferes with daily activities	Prevents daily activity
Redness at the vaccination site (erythema)*	Absent	< 10 mm	≥ 10 to ≤ 30 mm	> 30 mm
Induration/Swelling at the vaccination site*	Absent	< 10 mm	≥ 10 to ≤ 30 mm	> 30 mm

* Reaction to be measured in mm and recorded in the diary.

Solicited Systemic AEs

Solicited systemic AEs are defined and graded as follows:

Table 9.1.1.1-2 Solicited Systemic AEs

Solicited Systemic Adverse Event	Intensity Grading			
	None (Grade 0)	Mild (Grade 1)	Moderate (Grade 2)	Severe (Grade 3)
For all subjects:				
Fever (Axillary)	<99.5°F (<37.5°C)	≥99.5 – <100.4°F (≥37.5 – <38.0°C)	≥100.4 – <101.3°F (≥38.0 – <38.5°C)	≥101.3°F (≥38.5°C)
Nausea and/or Vomiting	None	Adverse events easily tolerated by the subject, causing minimal discomfort and does not interfere with daily activities	Adverse event sufficiently discomforting to interfere with daily activities	Adverse event prevents normal everyday activities or requires significant medical intervention
Diarrhea				
For subjects less than 36 months of age at the time of the first dose of study vaccine:				
Loss of appetite	None	Adverse events easily tolerated by the subject, causing minimal discomfort and does not interfere with daily activities	Adverse event sufficiently discomforting to interfere with daily activities	Adverse event prevents normal everyday activities or requires significant medical intervention
Irritability				
For subjects 36 months of age and older at the time of the first dose of study vaccine:				
Malaise and fatigue	None	Adverse events easily tolerated by the subject, causing minimal discomfort and does not interfere with daily activities	Adverse event sufficiently discomforting to interfere with daily activities	Adverse event prevents normal everyday activities or requires significant medical intervention
Headache				
Myalgia				

9.1.1.2 *Unsolicited AEs*

Unsolicited AEs are all other AEs and will be recorded electronically on the Other Body Symptoms Diary or recorded by investigational site staff in the eCRF.

The intensity/severity of unsolicited AEs will be assessed by the subject's parent(s)/guardian(s) and graded as follows:

- Mild:** Symptoms are easily tolerated and do not interfere with normal, everyday activities;
- Moderate:** Discomfort enough to cause some interference with normal, everyday activities;
- Severe:** Symptoms that prevent normal, everyday activities.

9.1.2 Adverse Events of Special Interest

An AE of special interest (AESI) is an event considered to be potentially associated with a product or product class. Monitoring and reporting AESIs is an important aspect relating to characterizing the safety profile of a product during clinical development and post-authorization phases. As such, AESIs reported during clinical development, are considered as a medically important events, worthy of reporting as a serious adverse event.

The proposed AESIs selected for QIV are consistent with those that are considered as either identified or potential risk associated with pharmacological class of influenza vaccines. To generate additional information on these rare adverse events, the occurrence of the following AESIs during the study must be reported:

- Febrile convulsion
- Febrile delirium
- Bell's palsy
- Demyelinating disorders
- Encephalomyelitis
- Guillain-Barré syndrome
- Optic neuritis
- Transverse myelitis
- Thrombocytopenia
- Vasculitis

All AESIs must be reported as the same manner as an SAE (see [Section 9.6](#)). All AESIs will be recorded in the AE and SAE pages of the eCRF. An SAE Reporting Form must be submitted to Seqirus Product Safety. On the SAE page of the eCRF, there is a seriousness criteria checklist (see [Section 9.1.3](#)). For AESIs, the "medically significant" criteria must be selected on the SAE criteria checklist. Any other criteria may also be selected as applicable.

Additional clinical information regarding an AESI may be requested from the investigator to ascertain the diagnosis according to the available scientific literature or established case definition.

All AESIs will be reviewed for signal evaluation by Seqirus Safety and assessed for expedited reporting.

9.1.3 Serious Adverse Events

A serious adverse event (SAE) is defined as any untoward medical occurrence that at any dose:

- **Results in death** – The event must be the cause of death for the SAE to meet this serious criterion;
- **Is life-threatening** – The term “life-threatening” refers to an event in which the subject was at risk of death at the time of the event; it does not refer to an event that hypothetically might have caused death if it had been more severe;
- **Requires in-patient hospitalization or prolongation of existing hospitalization** – Seqirus considers “hospitalization or prolongation of existing hospitalization” for at least 24 hours as the defining criterion for an SAE. Hospital admissions for planned surgery or for normal disease management procedures (eg, chemotherapy) are not considered as defining criteria for SAEs.
- **Results in persistent or significant disability or incapacity.**
- **Is a congenital anomaly or birth defect.**
- **Is medically significant** – A medically significant event is defined as an event that does not necessarily meet any of the SAE criteria, but which is judged by a physician to potentially jeopardize the subject or require medical or surgical intervention to prevent one of the above outcomes listed as an SAE criterion.
- **Is the suspected transmission of an infectious agent via a medicinal product.**

Adverse events that do not fall into the above categories are defined as nonserious AEs.

9.2 SEVERITY OF ADVERSE EVENTS

The severity of each AE (ie, nonserious and serious AEs) is to be assessed as follows:

Severity	Definition
Mild	A type of AE that is usually transient and may require only minimal treatment or therapeutic intervention. The event does not generally interfere with usual activities of daily living.
Moderate	A type of AE that is usually alleviated with additional specific therapeutic intervention. The event interferes with usual activities of daily living, causing discomfort but poses no significant or permanent risk of harm to the subject.
Severe	A type of AE that interrupts usual activities of daily living, or significantly affects clinical status, or may require intensive therapeutic intervention.

Clinical Data Interchange Standards Consortium Study Data Tabulation Model (CDISC SDTM) Severity Intensity Scale for Adverse Event Terminology

9.3 CAUSALITY OF ADVERSE EVENTS

The causal relationship of an AE to the Study Vaccine must always be assessed by the Investigator. All solicited local AEs will be assessed as related to the Study Vaccine. All other AEs will be classified as either **related** or **not related** to the Study Vaccine. If a causality assessment is not provided for an AE (including an SAE), the AE will be considered related to the Study Vaccine.

The degree of certainty with which an AE is attributed to the Study Vaccine or an alternative cause (eg, natural history of the underlying disease, concomitant therapy) will be determined by how well the event can be understood in terms of:

- Known pharmacology of the Study Vaccine;
- Clinically and/or pathophysiologically plausible context;
- Reaction of a similar nature previously observed with similar products, or reported in the literature for similar products as being product related (eg, headache, facial flushing, pallor);
- Plausibility supported by the temporal relationship (eg, the event being related by time to administration or termination of treatment with the Study Vaccine, drug withdrawal or reproduced on rechallenge).

9.4 OBSERVATION PERIOD FOR ADVERSE EVENTS

The observation period for AE reporting in an individual subject will start at the time of giving written informed consent for participation in the current study and finish at 28 days after the last vaccination (the Exit Visit).

The observation period for SAE and AESI reporting in an individual subject will start at the time of giving written informed consent for participation in the current study and finish 180 days after the last vaccination.

If the Investigator becomes aware of an SAE or AESI that has started after the observation period has finished, and the event is considered by the Investigator to be causally related to the Study Vaccine, then this must also be reported to Seqirus Safety - see [Section 9.6](#) (Serious Adverse Event Reporting).

9.5 ADVERSE EVENT REPORTING

9.5.1 Adverse Events

At each clinical evaluation, the investigator (or delegate) will determine whether any AEs have occurred. AEs will be recorded in the AE page of the eCRF. If known, the medical diagnosis of an AE should be recorded in preference to the listing of individual signs and symptoms.

If, during the study period, a subject presents with a relevant medical history that was not noted at the time of study entry, the condition should be retrospectively recorded in the Medical History section of the eCRF.

For AE reporting, the study period is defined as that time period from the signature of the informed consent form through the Exit Visit. Therefore, events that occur before the initial screening visit will be recorded in the medical history and events that occur after the signing of the informed consent form will be recorded as an AE.

9.5.2 Adverse Events of Special Interest

All AESIs must be reported as the same manner as an SAE (see [Section 9.6](#))

9.6 SERIOUS ADVERSE EVENT REPORTING

This study will comply with all applicable regulatory requirements and adhere to the full requirements of ICH Topic E2A (Clinical Safety Data Management: Definitions and Standards for Expedited Reporting).

For SAEs occurring during the study, the investigator or delegate will enter all relevant information in the AE/SAE page of the eCRF. If entry into the eCRF is not possible (eg, because of an internet access problem), a paper SAE data collection form must be completed.

All SAEs that occur during the observation period for SAEs (from the time of Informed Consent to Day 180, see section 9.4), whether or not considered causally related to Study Vaccine, MUST BE REPORTED IMMEDIATELY (within 24 hours of becoming aware of the event) to Seqirus. Adverse events occurring in the period between the time of provision of written informed consent and the first exposure to the Study Vaccine that meet one or more of the seriousness criteria for AEs must be reported to Seqirus Safety in the same manner as other SAEs and will be included in the clinical study database.

Any SAE that occurs after the Day 180 Follow-up Phone call that is considered to be causally related to the investigational product must be **reported immediately (ie, within 24 hours of the Investigator becoming aware of the event) to Seqirus.**

Prompt notification is essential so that regulatory requirements for SAE reporting and ethical obligations to the subjects involved in the study can be met.

Guidance for reporting SAEs will be provided to study sites before the study starts. Details for reporting of SAEs will be described in the SAE reporting plan and eCRF completion guidelines.

Seqirus Safety contact details for SAE reporting:

Facsimile (US):	[name]
Email:	[contact]

9.6.1 Requirements for Immediate Reporting of Serious Adverse Events

For SAEs occurring during the study the Investigator/delegate will complete the AE/SAE page and other relevant pages of the eCRF. The Investigator/delegate must include all relevant information regarding the event.

The minimum reporting requirements for immediate reporting of SAEs include:

- Identifiable subject.
- Suspected medicinal product and / or procedure.
- Event term.
- Identifiable reporting source.

If the minimum requirements for reporting are fulfilled, the Investigator should not wait to receive additional information to fully document the event before notifying Seqirus.

In addition, the Investigator must:

- Report all SAEs to the relevant IRB / IEC within the timeframe specified by the IRB / IEC.
- Submit follow-up reports to Seqirus Safety until the SAE has resolved, or, in the case of permanent impairment, until stabilized.
- Ensure that the causality assessment for all SAEs is entered in the eCRF.

When submitting SAE reports and any other related reports (eg, discharge summaries) to Seqirus, subjects should be identified only by their subject number and study number. The investigator should not include the subject's name, date of birth, or address.

In cases of death, the investigator should supply Seqirus and the IRB (as applicable) with any additional information as it becomes available (eg, autopsy reports and detailed medical reports).

The procedure to be followed if an ongoing AE becomes an SAE after the end of the observation period for AEs is described in [Section 9.9](#) (Follow-up of Adverse Events).

9.7 OTHER SIGNIFICANT EVENT REPORTING - ENROLLMENT HALTING RULES

An independent Data Safety Monitoring Board (DSMB) will monitor subject safety during the study. The DSMB will comprise clinical study experts with experience in vaccine studies and safety assessment. The DSMB will provide recommendations for stopping or continuing the study based on the assessment of study safety data according to processes defined in the study protocol and the DSMB Charter.

Enrolment into the study and study vaccination will be halted for DSMB review/ recommendation for continuation if during the 7 days after vaccination (Day 1 to Day 7) any of the following occur:

- One or more subject experiences an AE that is serious, unexpected, and is assessed as related to Study Vaccine;
- One or more subject experiences an AE that is life-threatening or causes death;
- One or more subject experiences a serious febrile AE, defined as any AE meeting seriousness criteria that is also associated with a fever of $\geq 101.3^{\circ}\text{F}$ / $\geq 38.5^{\circ}\text{C}$ (axillary).
- One or more of the subjects experiences a severe (grade 3)
 - allergic reaction (eg, hives, angioedema, allergic asthma, systemic anaphylaxis);
 - Vaccine-related injection site ulceration, abscess, or necrosis;

Additionally, enrolment into the study and study vaccination will be halted pending review by the DSMB if during Day 1 to Day 7, the following defined halting rule criteria are met in either study cohort (6 months through 35 months or 36 months through 59 months):

- $\geq 5\%$ of subjects enrolled to date, with concurrent grade 3 pain, erythema, and induration (a cellulitis-like reaction) that is assessed as related to Study Vaccine.

(Note: If the total number of subjects enrolled to date is less than 60, a minimum of 3 subjects experiencing a concurrent severe vaccine-associated pain, erythema or induration will be needed to halt further enrolment);

- $\geq 5\%$ of subjects enrolled to date experience a fever of $\geq 101.3^{\circ}\text{F}$ / $\geq 38.5^{\circ}\text{C}$ (axillary) that is assessed as related to Study Vaccine.

(Note: if the total number of subjects enrolled to date is less than 60, a minimum of 3 subjects is required to trigger the halt).

In addition, the DSMB chair will be immediately notified of any SAE, regardless of causality or expectedness assessment, occurring during Day 1 to Day 7. The DSMB chair will then make a determination regarding the necessity of a DSMB meeting and/or study halt in response to these events.

Any decision to terminate the study will be made by Seqirus in consultation with the DSMB, and the study investigators.

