 - *Seroconversion.* For each strain the subjects will be classified as 'seroconverted' if either they have a prevaccination HI antibody titer < 1:10 and a postvaccination HI antibody titer \geq
-

1:40 or a prevaccination HI antibody titer \geq 1:10 and a \geq 4-fold increase in postvaccination HI antibody titer. Otherwise they will be classified as ‘not seroconverted’;

- *Seroprotection*. For each strain a subject will be classified as ‘seroprotected’ if their HI antibody titer \geq 1:40 at Days 1 and the Study Exit Visit. If they do not have both antibody titers \geq 1:40 they will be classified as ‘not seroprotected’;
- *Fold increase*. For each strain the fold increase for each subject will be calculated by taking the ratio of the postvaccination antibody titer over the prevaccination antibody titer;

Covariate adjusted analyses will be performed as outlined in the Statistical Analysis Plan (SAP).

Immunogenicity Analyses (Day 1 and Study Exit Visit):

Immunogenicity analyses in terms of HI antibody titers specific for the virus strains included in the vaccines will be performed on serum specimens taken at Day 1 (Visit 1) and at the Study Exit Visit (Visit 2 – single dose schedule or Visit 3 – two-dose schedule).

Safety Assessments

Safety will be assessed through solicited local reactions, solicited systemic AEs, unsolicited AEs, and SAEs.

Type, frequency and intensity of solicited local reactions through Day 7 (Day 1, 2, 3, 4, 5, 6, 7) following each study vaccination dose. These include pain, erythema/redness, and induration/swelling.

Frequency of cellulitis-like reaction for 28 days following each vaccination. Cellulitis-like reaction is defined as the concurrent presence of grade 3 injection site pain, erythema/redness and induration/swelling.

Type, frequency, duration and intensity of solicited systemic AEs through to Day 7 (Day 1, 2, 3, 4, 5, 6, 7) following each study vaccination dose. These include headache, malaise and fatigue, myalgia, fever, diarrhea, and nausea and/or vomiting for children 36 months through 59 months of age, and fever, diarrhea, nausea and/or vomiting, loss of appetite, and irritability for children 6 months through 35 months of age.

Frequency of antipyretic use in the 7 days after each vaccination dose

Type, frequency, duration and intensity of unsolicited AEs for at least 28 days following each study vaccination dose.

	Frequency of SAEs and AESIs for at least 180 days following the last vaccination dose.

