Additionally, enrollment into the study and study vaccination will be halted pending review by the DSMB if during Day 1 to Day 7, the following defined halting rule criteria are met in either study cohort (6 months through 35 months or 36 months through 59 months):

- $\geq 5\%$ of subjects enrolled to date with concurrent grade 3 pain, erythema, and induration (a cellulitis-like reaction) that is assessed as related to Study Vaccine.
(Note: If the total number of subjects enrolled to date is less than 60, a minimum of 3 subjects experiencing a concurrent severe vaccine-associated pain, erythema or induration will be needed to halt further enrollment);
- $\geq 5\%$ of subjects enrolled to date, experience a fever of $\geq 101.3^{\circ}\text{F}$ [$\geq 38.5^{\circ}\text{C}$] (axillary) that is assessed as related to Study Vaccine.
(Note: if the total number of subjects enrolled to date is less than 60, a minimum of 3 subjects is required to trigger the halt).

In addition, the DSMB chair will be immediately notified of any SAE, regardless of causality or expectedness assessment, occurring during Day 1 to Day 7. The DSMB chair will then make a determination regarding the necessity of a DSMB meeting and/or study halt in response to these events.

Data Safety Monitoring Board

An independent DSMB will monitor subject safety during the study. The DSMB will comprise clinical study experts with experience in vaccine studies and safety assessment. The DSMB will provide recommendations for stopping or continuing the study based on the assessment of study safety data according to processes defined in the study protocol and the DSMB Charter.

Schedule of Assessments – Single Dose Regimen

Assessment		Visit 1	Phone call	Visit 2	Phone call	Phone call
	Pre-Study	Vaccination	Diaries Reminder	Exit Visit	SAE Follow-up	SAE Follow-up
	Day -7 to -1	Day 1	Day 3 + 2	Day 29 + 4	Day 90 + 7	Day 180 + 7
Invitation to participate		✓ ¹				
Informed consent		✓ ¹				
Demographics and influenza vaccination history		✓ ¹				
Medical history and baseline medication use		✓ ¹				
Targeted physical examination (if necessary)		✓ ¹		✓		
Body weight		✓ ¹				
Axillary temperature		✓				
Review of eligibility criteria		✓				
Blood sample for immunogenicity testing		✓		✓		
Vaccination		✓				
Provision of study supplies and instructions		✓				
Solicited Diary review			✓	✓		
Unsolicited/Concomitant Medications Diary review			✓	✓		

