3.6 STUDY MONITORING PROCEDURES

3.6.1 Data and Safety Monitoring Board

An independent DSMB will monitor subject safety during the study. The DSMB will comprise clinical study experts with experience in vaccine studies and safety assessment. The DSMB will provide recommendations for stopping or continuing the study based on the assessment of study safety data according to processes defined in the study protocol and the DSMB Charter.

DSMB will review available safety data and provide recommendations after approximately one third of subjects (or a minimum of 300 subjects) in the 36 through 59 months age group have received the first vaccination and have had an opportunity to enter at least 7 days of safety data postvaccination.

A second safety data cut will be performed when approximately one third of subjects (or a minimum of 300 subjects) in the 6 through to 35 months age cohort have received the first vaccination and have had an opportunity to enter at least 7 days of safety data postvaccination. A DSMB meeting will be convened once tables and listings are produced to review and assess the available safety data. Recruitment in both age cohorts will not be halted during the period of the data cut and DSMB review.

Adverse events contributing to enrollment halting rules (see [Section 9.7](#)) will be reported to the Sponsor automatically from the electronic Case Report Form (eCRF) in the clinical database. If enrollment halting rules are met, enrollment into the study will be halted pending DSMB review of the safety data, and Sponsor consideration of DSMB recommendations following the review. Independent safety monitors at each site are not required.

The DSMB will:

- Be responsible for providing recommendations to Seqirus surrounding study conduct matters that affect safety.
- Review the safety data at designated time points and potentially ad-hoc time points and identify if significant safety concerns arise during the study.
- Review data that may affect subject continuation.
- Make recommendations regarding study progression.

The DSMB will be constituted and conducted in accordance with the FDA *Guidance for Clinical Trial Sponsors. Establishment and Operation of Clinical Trial Data and Monitoring Committees. March 2006.*

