The site should perform an assessment to attempt to confirm a postvaccination ILI at the time of the ILI-assessment visit (the subject's temperature and clinical symptoms should be assessed). Additionally, the site may also confirm a postvaccination ILI through review of the AE diaries and/or illness history reported verbally by the subject at a time prior to the ILI visit. Information related to confirmation of a postvaccination ILI should be recorded in the subject's source notes.

Upon confirmation that the ILI case definition is met, the subject's temperature will be assessed and attempts will be made to diagnose influenza viral infection by obtaining nasal and throat swab specimens. These will be analyzed for laboratory confirmation of influenza A and/or B by Reverse Transcriptase Polymerase Chain Reaction (RT-PCR).

Laboratory confirmation is more likely for specimens collected within approximately 3-4 days of illness onset, but nasal and throat swabs should be collected if the ILI assessment visit occurs up to 7 days after illness onset, to try to identify as many cases of laboratory confirmed influenza infection as possible. After 7 days following illness onset, the Investigator may choose whether to collect nasal and throat swabs, based on their clinical judgement of the potential value of testing specimens due to ongoing ILI symptoms.

Refer to the study-specific Nasal and Throat Swab Specimen Collection Instructions, for further details on collection, storage, handling and transportation of the nasal and throat swab specimens to the laboratory.

Unscheduled Visit – Cellulitis-like Reaction

Subjects reporting signs/symptoms of a Cellulitis-like Reaction between Day 1 and Study Exit Visit will be asked to attend an additional clinic visit within 24 hours (up to 3 days if on a weekend) of the symptoms meeting the definition of a cellulitis-like reaction.

The criteria for a Cellulitis-like Reaction are concurrent presence of all three of the following:

- Grade 3 injection site pain;
- Grade 3 injection site erythema;
- Grade 3 injection site induration.

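### The under-60 note to the cellulitis-like-reaction halting rule counts severe pain, erythema *or* induration, while the rule it qualifies and every definition of the event require all three signs together

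*Protocol*

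**What the plan says.** Protocol Section 9.7 has two percentage-based halting rules, each assessed over Day 1 to Day 7 and in either age cohort. The first halts enrolment and vaccination, pending DSMB review, when at least 5% of subjects enrolled so far are recorded "with concurrent grade 3 pain, erythema, and induration (a cellulitis-like reaction) that is assessed as related to Study Vaccine". The note beneath it applies when fewer than 60 are enrolled and says "a minimum of 3 subjects experiencing a concurrent severe vaccine-associated pain, erythema or induration will be needed to halt further enrolment". The synopsis repeats rule and note with the same *or*.

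The second rule covers fever of at least 38.5°C. Its note for fewer than 60 enrolled says only that "a minimum of 3 subjects is required to trigger the halt". It changes the count and leaves the event alone.

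Elsewhere the event is defined consistently:

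- Protocol synopsis (Safety Assessments) and Section 10.3: "Cellulitis-like reaction is defined as the concurrent presence of grade 3 injection site pain, erythema/redness and induration/swelling".
- Protocol synopsis (unscheduled visit), Protocol Section 8.4.3 and SAP Section 3.3.3: "The criteria for a Cellulitis-like Reaction are concurrent presence of all three of the following", followed by grade 3 pain, erythema and induration.
- SAP Section 4.7.4.3: the same three grade 3 signs, concurrently.

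Protocol Section 3.6.1 adds that events contributing to the halting rules "will be reported to the Sponsor automatically from the electronic Case Report Form (eCRF) in the clinical database".

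**The concern.** One halting rule carries two event definitions: *and* in the rule, *or* in the note that modifies it. Taken literally, the note lets a subject with one severe local sign count towards the three.

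The word *vaccine-associated* does not narrow this, because Protocol Section 9.3 treats all solicited local events as related. Nor does *severe*, because the grading table in Section 9.1.1.1 makes severe and grade 3 the same thing.

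This is an operative threshold that stops enrolment and vaccination, and its contributing events are reported automatically. Anyone programming a flag or drafting a charter from Section 9.7 should not have to choose between two definitions. What is at stake is an unnecessary halt for DSMB review early in enrolment.

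**Working it through.** **Inputs.** From Protocol Section 9.7: the 5% threshold, the floor of 3 subjects, and the under-60 condition. From Protocol Sections 3.5 and 11.1: planned enrolment of 2222. From Section 3.1: the younger cohort opens only after DSMB review of about one third (or at least 300) of the older cohort.

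**1. The plan's own number.** 5% of 60 is 0.05 × 60 = 3, and 3/59 = 5.08%. The floor of 3 therefore joins the 5% rule exactly at 60 subjects. The count is right and only the event is mismatched.

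**2. Which word is wrong.** The rule and all the definitions listed above require three signs. The note itself says *concurrent*, which has no clear meaning for a single sign. The parallel fever note does not alter its event. All of this points to *and* as the intention.

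**3. When the wordings give different decisions.** Let n be the number enrolled and counted, a the subjects with all three signs, and i the other subjects with at least one grade 3 local sign. For n < 60:

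*Reading A: the note is a minimum on top of the 5% rule* (suggested by its phrasing that 3 are needed).

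- *And* halts if a/n ≥ 0.05 and a ≥ 3. *Or* halts if a/n ≥ 0.05 and a + i ≥ 3.
- a = 0: neither halts. a ≥ 3: they agree.
- a = 1: they differ if i ≥ 2 and n ≤ 20 (1/20 = 5.00%, 1/21 = 4.76%).
- a = 2: they differ if i ≥ 1 and n ≤ 40 (2/40 = 5.00%, 2/41 = 4.88%).
- The window is the first 40 subjects counted.

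*Reading B: the note is a standalone trigger below 60.*

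- *And* halts if a ≥ 3. *Or* halts if a + i ≥ 3.
- They differ whenever a ≤ 2 and a + i ≥ 3, including a = 0.
- The window is the first 59 subjects counted.

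**4. Size of the window.** The note refers to the total enrolled so far, while the lead-in assesses each cohort. If the total means the study, the note can apply only once, to the older cohort, because the younger cohort opens well after 60 subjects.

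| | Per cohort (two windows) | Once for the study |
|---|---|---|
| Reading A | 2 × 40 = 80; 80/2222 = 3.6% | 40/2222 = 1.8% |
| Reading B | 2 × 59 = 118; 118/2222 = 5.3% | 59/2222 = 2.7% |

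These percentages show how long the wording could matter. They are not the chance that it does.

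**5. Direction.** Under either reading, any data that halt with *and* also halt with *or*, since a ≥ 3 implies a + i ≥ 3. The slip can add a halt but cannot remove one.

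**6. Chance of an altered halt.** The documents give no grade 3 local reaction rates for this population, so this cannot be estimated. As illustration only, under Reading B with 59 subjects, the binomial chance of at least 3 with any severe sign is 11.4%, 57.1% or 94.3% if that rate is assumed to be 2%, 5% or 10%. The chance of at least 3 with all three signs is 0.33% or 2.1% if that rate is assumed to be 0.5% or 1%. The spread shows that the answer depends wholly on the assumed rates.

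**The case against.** The strongest reply is that this is a one-word copy-edit with no real ambiguity. The note sits inside the bullet that defines the event, keeps the word *concurrent*, and is surrounded by definitions that all agree.

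The visible data capture also refers to the defined event. SAP Section 3.5.2.3 lists a data item asking whether the cellulitis-like-reaction criteria were confirmed. Protocol Section 8.4.3 and SAP Section 3.3.3 send possible cases to a visit that checks the three-sign definition. A halt leads to DSMB review, and termination is a separate decision. Life-threatening, fatal and serious febrile events have their own single-case triggers in Section 9.7, and the DSMB chair is told of every serious event in Days 1 to 7.

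Most of this stands. The intention is clear and the consequence is small. It does not remove the point: the error is in the current text in both places where the rule is stated. The data item and visit do not show how the halting flag was programmed, and the DSMB Charter, to which SAP Section 4.2 refers halting triggers, is not among the documents.

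A reader might infer that isolated severe signs could never halt the trial by themselves and that only the first 40 subjects of each cohort are exposed. That holds only if the note adds to the 5% rule and its count is per cohort, and the text settles neither. A reader might equally infer that any three severe local signs would certainly stop enrolment. That needs Reading B, which the note's phrasing makes less natural.

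**Conclusion.** The point holds as a minor inconsistency in an operative safety rule. The under-60 note names a broader event than the rule it qualifies and than every definition in the protocol and SAP.

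Its reach is the first 40 or 59 subjects counted, once or in each cohort: 40, 59, 80 or 118 of 2222, depending on two readings that the text leaves open. The likely effect is an unneeded pause for DSMB review, not missed harm. Alpha, power, the analysis populations and the safety tables are unaffected, since SAP Section 4.7.4.3 uses the three-sign event.

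The documents do not support going further and saying that the wrong event was monitored. What can be seen of the data capture points the other way, and the Charter and the flag cannot be seen.

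**What to change.** In Protocol Section 9.7 and in the synopsis, reword the end of the note to: *a minimum of 3 subjects with a cellulitis-like reaction (concurrent grade 3 pain, erythema and induration) assessed as related to Study Vaccine will be needed to halt further enrolment*. Then check that the DSMB Charter and any eCRF flag use the same event.

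The change also makes the choice between Readings A and B immaterial for the three-subject threshold: with three all-three cases and at most 59 enrolled, the proportion is at least 3/59 = 5.08%, so the 5% criterion is met anyway.

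Stating whether the under-60 count is per cohort or for the whole study would be a useful separate clarification, but the correction does not depend on it.

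The cost is a wording change in two places and a document check, with no change to design, sample size or analysis.
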